5.8.2. Clinical Laboratory Measurements

For the respective EAP, FUP, and overall study period, clinical laboratory parameter actual values (quantitative) and change from baseline values will be descriptively summarized at baseline and each post-baseline visit by treatment group.

Individual subject laboratory parameter measurements will be additionally evaluated by PCSV criteria (See Appendix 10.3), specifically identifying subjects with at least one post-baseline measurement that meets the PCSV criteria. These laboratory parameters will be presented by the biological functions. The incidence of PCSVs at any time during the respective treatment-emergent periods (EAP and FUP) will be summarized regardless of the baseline level, and again according to the following baseline categories:

- Normal (according to PCSV criterion/criteria)/missing
- Abnormal according to PCSV criterion or criteria

Shift tables based on baseline normal/abnormal and other tabular and graphical methods may be used to present the results for laboratory tests of interest.

Subject listings of laboratory measurements that meet PCSV criteria will be provided for the report appendix.

A listing of all women of childbearing potential with a confirmed serum pregnancy test during the study will be provided.

5.8.3. Analysis of Vital Signs

For the respective EAP, FUP, and overall study period, the vital sign actual values (quantitative) and change from baseline values will be descriptively summarized at baseline and each post-baseline visit will be summarized by treatment group.

Individual subject laboratory parameter measurements will be additionally evaluated by PCSV criteria (See Appendix 10.3), specifically identifying subjects with at least one post-baseline measurement that meets the PCSV criteria.

Subject listings of vital sign measurements that meet PCSV criteria will be provided for the report appendix.

5.8.4. Analysis of Other Safety Variables - Abnormal Findings during SARS-CoV-2 Infection-related Medically Attended Visits

For subjects who become SARS-CoV-2 positive and require medically attended visits to the emergency department (ED), urgent care center (UCC), or hospitalization starting from the timepoint of SARS-CoV-2 RT-qPCR positive and through the end of the study, will have the following parameters or occurrences (worst or most abnormal finding) during the medically attended visit/stay collected (eCRF).

- Nature of visit (ED, UCC, hospital stay)
- Abnormal vital signs: respiratory rate ≥ 30 per minute, heart rate ≥ 125 per minute, peripheral capillary oxygen saturation (SpO_2) $\leq 93\%$ on room air at sea level, or oxygen partial pressure (PaO_2)/fractional inspired oxygen (FiO_2) < 300 mm Hg
- Respiratory failure: needing high-flow oxygen, noninvasive ventilation, mechanical ventilation, extracorporeal membrane oxygenation (ECMO)
- Evidence of shock: systolic blood pressure (SBP) < 90 mm Hg, diastolic blood pressure (DBP) < 60 mm Hg or requiring vasopressors (Note: *these limits for abnormal vital signs are for adult and adolescent subjects.*)
- Multiorgan dysfunction: Significant acute renal, hepatic, or neurologic dysfunction
- Multisystem inflammatory syndrome in children (MIS-C). (Note: for pediatric subjects < 12 years only.)
- Admission to an ICU

Number and percentage of subjects who presented at least one of abnormal findings and then by each of these 5 abnormal findings will be provided by treatment group and TEAE period (TEEAP, TEFUP, and overall study period). Within each abnormal findings, number and percentages of subjects will also be reported for each observed criterion.

A listing of subjects who have any of these abnormal findings with any SARS-CoV-2 infection-related medically-attended visit will be provided including the corresponding study period information.

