### 5.3. Safety Variables

Safety variables include recording, measurements, or laboratory test results for individual subjects of the following: TEAEs; vital signs including heart rate, blood pressure, respiration rate, and body temperature, physical examination findings; results of laboratory tests including hematology, blood chemistry, and urinalysis (only for adult/adolescent subjects). In addition, subjects with a positive RT-PCR result and a medically attended visit (ED, UCC, hospitalization) will be assessed for occurrence (worst or most abnormal finding) of abnormal vital signs, respiratory failure, evidence of shock, multiorgan dysfunction and admission to ICU; Section [9.2.3](#)).

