Any subject who, between the study visits, develops fever, an acute respiratory illness, symptoms related to MIS-C (pediatric subjects <18 years only), or other symptoms that they may feel could be related to COVID-19 should alert the study staff immediately. If the subject experiences a true medical emergency, they should visit their local hospital ED or call the local emergency telephone number (eg, 911 in North America) and contact the clinical site personnel later. The subjects' symptoms must be evaluated by the investigator or designee, which can occur through site visit, mobile unit, home visit, telemedicine, etc. If the investigator or designee deems the subject's signs/symptoms require the collection of biological samples for central lab testing to assess or confirm SARS-CoV-2 infection, the subject will be advised to provide NP sample. The subject may also be asked to provide blood samples if it corresponds to a scheduled visit, according to the Schedule of Events (specified in Section 9.1). If a subject is hospitalized for suspected COVID-19, every effort should be made by the site personnel to collect, as soon as possible, a NP swab sample for central lab SARS-CoV-2 RT-qPCR testing. In subjects where it is not possible to have samples collected for assessment in the central laboratory, study site personnel will attempt to obtain and record information about all SARS-CoV-2 assays conducted in other medical facilities, including result(s), name of the assay(s) and whether the laboratory(ies) conducting the assays is a CLIA certified (or equivalent) laboratory. The laboratory report for a positive SARS-CoV-2 test result, including the name of the test as well as information about laboratory certification, should be collected and stored as source documentation at the site. The positive SARS CoV-2 assay result will be recorded as concomitant procedures related to the COVID-19 AE. Details on any symptoms and medically attended visits will also be collected.

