### 9.2.2.3. Assessment of Medically Attended Visits

Only for RT-qPCR positive subjects (cohort A, cohort A1, cohort B, and cohort B1): Subjects and/or their parent/guardian (as appropriate) who are or become SARS-CoV-2 RT-PCR positive will be queried on any SARS-CoV-2 infection-related medically attended visits to the ED, UCC, or hospitalization (Table 3 and Table 5). The assessment of medically attended visits to ED, UCC or hospitalization will be performed from the time the subject first becomes SARS-CoV-2 RT-qPCR positive or from the time they develop symptoms suspected to be COVID-19 (later confirmed by RT-qPCR positive results) until the subject has had 2 negative tests or COVID-19 related symptoms have resolved (whichever lasts longer), or until the end of study visit. Details associated with any SARS-CoV-2 infection-related medically-attended visit will be recorded and will include at minimum:

- Nature of the visit (ED, UCC, hospital stay)
- Date and length of visit
- Primary reason for the visit should be recorded as an adverse event
- Assessment of the following parameters or occurrences (worst or most abnormal finding) during the medically attended visit/stay:
  - Abnormal vital signs: respiratory rate  $\geq 30$  per minute, heart rate  $\geq 125$  per minute, peripheral capillary oxygen saturation ( $\text{SpO}_2$ )  $\leq 93\%$  on room air at sea level, or oxygen partial pressure ( $\text{PaO}_2$ )/fractional inspired oxygen ( $\text{FiO}_2$ )  $< 300$  mm Hg)  
*Note: these limits for abnormal vital signs are for adult and adolescent subjects.*
  - Respiratory failure: needing high-flow oxygen, noninvasive ventilation, mechanical ventilation, extracorporeal membrane oxygenation (ECMO)
  - Evidence of shock: systolic blood pressure (SBP)  $< 90$  mm Hg, diastolic blood pressure (DBP)  $< 60$  mm Hg, or requiring vasopressors  
*Note: these limits for abnormal vital signs are for adult and adolescent subjects.*
  - Multiorgan dysfunction: Significant acute renal, hepatic, or neurologic dysfunction
  - Multisystem inflammatory syndrome in children (MIS-C)  
*Note: for pediatric subjects  $< 18$  years only*
  - Admission to an ICU

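### SAP 5.8.4 limits MIS-C to subjects under 12 and counts 5 findings where it lists 6, whereas protocol 9.2.2.3 collects MIS-C under 18, so an adolescent case may be missing from that table's MIS-C row.

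*SAP*

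**What the plan says.** SAP 5.8.4 covers subjects who become SARS-CoV-2 positive and have an emergency department, urgent care or hospital visit. It gives seven bullets. The first, "Nature of visit (ED, UCC, hospital stay", describes the visit. The other six are abnormal vital signs, respiratory failure, shock, multiorgan dysfunction, MIS-C and ICU admission. The MIS-C bullet carries the age note "Multisystem inflammatory syndrome in children (MIS-C). (Note: for pediatric subjects < 12 years only". The SAP then plans counts and percentages of subjects with at least one finding, "then by each of these 5 abnormal findings will be provided by treatment group and TEAE period", followed by a subject listing.

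Protocol 9.2.2.3 defines the same assessment. Under MIS-C it says "Note: for pediatric subjects $< 18$ years only". Protocol 6.1.5 uses the same limit when it tells subjects to alert staff to "symptoms related to MIS-C (pediatric subjects <18 years only"; the synopsis and section 6.1.4 do likewise.

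Protocol 5.3 names the findings assessed at these visits as "abnormal vital signs, respiratory failure, evidence of shock, multiorgan dysfunction and admission to ICU". MIS-C is not among them.

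SAP 1.2.4 states that nothing has been changed relative to protocol amendment 6.

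**The concern.** Two statements in SAP 5.8.4 disagree with their surroundings. The age note is narrower than the protocol's collection rule for the same item, with no reason given and no deviation declared. The number of findings to be tabulated does not match the list directly above it.

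Both bear on the only item in that table that is specific to subjects under 18. Subjects aged 12 to under 18 belong to cohorts A and B, and SAP 5.8 makes them a separate safety age group. At stake is whether a rare but serious paediatric event, which sites are told to record in adolescents, has a row in the table built for it.

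**Working it through.** No sample-size or error-rate formula applies. The check is a count and a side-by-side reading.

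**Count.** The plan's stated figure is 5.

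- All bullets in SAP 5.8.4: 7.
- Without nature of visit, which is not a finding: 7 − 1 = 6.
- Without MIS-C as well: 6 − 1 = 5, and the five that remain are those named in protocol 5.3.

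The stated 5 is therefore not reproduced from the SAP's own list. It is reproduced by leaving MIS-C out, as protocol 5.3 does. That section is a plausible source of the number, but the documents do not say so.

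**Age limit for MIS-C.**

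| Place | What it governs | Limit |
|---|---|---|
| Protocol synopsis, 6.1.4, 6.1.5 | Symptoms that should prompt a call to the site | under 18 |
| Protocol 9.2.2.3 | Assessment at medically attended visits | under 18 |
| Protocol 5.3 | List of safety findings | MIS-C not listed |
| SAP 5.8.4 | Collection and summary of the same findings | under 12 |

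Only protocol 9.2.2.3 is in direct conflict with SAP 5.8.4, because both describe the same assessment. The symptom-alert passages show the limit used elsewhere in the protocol but do not define MIS-C data collection. The gap between the two limits is the age range 12 to under 18.

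**What a programmer could produce.**

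| Reading of SAP 5.8.4 | MIS-C under 12 | MIS-C at 12 to under 18 |
|---|---|---|
| Six rows, age note applied | in MIS-C row | not in MIS-C row |
| Five rows, as in protocol 5.3 | no MIS-C row | no MIS-C row |
| Six rows, age note ignored when tabulating | in MIS-C row | in MIS-C row, if recorded |

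Two of the three readings lose the adolescent case from the MIS-C row, and one of those also loses the younger children. The text does not settle which reading applies.

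**Who is affected.** To fall in the gap, a subject must be aged 12 to under 18, be RT-qPCR positive, have an infection-related emergency, urgent care or hospital visit, and have MIS-C. The documents give no number of adolescents and no expected MIS-C rate, so no count can be derived.

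**The case against.** The strongest reply is that nothing is certain to be lost. The age note sits in the list of what is collected on the eCRF, while the sentence that defines the table has no age filter. Collection is governed by the protocol, which reaches to under 18, and the SAP nowhere says to discard an adolescent entry. This stands in part. It is why the conclusion is that a case may be missing from the row. It does not remove the conflict, because the table is defined from that same list and the count of five does not fit it.

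A reader might go further and infer that adolescent MIS-C would drop out of the safety report, or that the comparison of severity between arms would be incomplete for adolescents. The documents do not support that. Protocol 9.2.2.3 requires the main reason for the visit to be recorded as an adverse event. A hospital admission of any duration is a serious adverse event under protocol 10.2.2. SAP 5.8.1 tabulates adverse events by preferred term and by severity, and serious events separately, and SAP 5.8 repeats the safety analysis for ages 12 to under 18. An adolescent with MIS-C who also meets the criteria for shock, respiratory failure, organ dysfunction or ICU admission would be counted in those rows, in the at-least-one total and in the listing. The SAP describes this output as a summary of abnormal findings, not as a severity analysis.

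It would also be wrong to say that every subject aged 12 to under 18 is affected; the group is the narrow one set out in the check above.

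**Conclusion.** The inconsistency is real and is undeclared. SAP 5.8.4 contradicts protocol 9.2.2.3 on the age limit and contradicts its own list on the number of findings. Followed literally, it gives an adolescent MIS-C case no place in the MIS-C row; if the five findings are those of protocol 5.3, no child has one.

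The size is minor. One descriptive safety table is affected. The at-least-one total and the listing are affected only for a case that meets no other finding.

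The conclusion assumes that the SAP text would be programmed as written and that the eCRF follows protocol 9.2.2.3. The eCRF is not among the documents. If its MIS-C field were itself limited to under 12, changing the SAP alone would not recover the item for adolescents.

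**What to change.** In SAP 5.8.4, set the age note on MIS-C to under 18 years, in line with protocol 9.2.2.3, and change the number of abnormal findings from 5 to 6 so that MIS-C has its own row. Reconcile protocol 5.3 with 9.2.2.3 by adding MIS-C to its list, or record in the SAP that 9.2.2.3 is the governing list. Confirm that the eCRF field for MIS-C is open to all subjects under 18.

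The SAP change is two small edits and one table row, with no new data and no effect on any hypothesis test. It should be made before the first-step database lock, which SAP section 1 sets as the deadline for the final plan. The protocol wording can follow at the next amendment or be handled by a note to file.

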5.9. Analysis of Pharmacokinetic Data

5.9.1. Analysis of drug concentration data

Concentrations of REGN10933 and REGN10987 over time will be summarized by descriptive statistics for each cohort. No formal statistical hypothesis testing will be performed.

Dense PK sentinel cohort

The PK parameters to be determined after the first dose for REGN10933 and REGN10987 may include, but are not limited to:

- C_{\max}
- C_{\max}/Dose

- t_{\max}
- t_{last}
- C_{last}
- AUC_{inf}
- $AUC_{\text{inf}}/\text{Dose}$
- $t_{1/2}$
- C_{28} (concentration in serum 28 days after dosing)

Selected PK parameters will be summarized by descriptive statistics for each cohort. Results from two different cohorts may be combined if appropriate.

Sparse PK

Concentrations of REGN10933 and REGN10987 in serum over time will be summarized by descriptive statistics for each cohort. No formal statistical hypothesis testing will be performed.

5.10. Analysis of Immunogenicity Data

The immunogenicity variables described in Section 4.8 will be summarized using descriptive statistics.

Immunogenicity will be characterized by ADA responses and titers observed in subjects in the ADA analysis set. ADA response categories and titer categories are defined as follows:

ADA response categories:

- ADA Negative, defined as ADA negative response in the ADA assay at all time points, regardless of any missing samples.
- Pre-existing immunoreactivity, defined as either an ADA positive response in the ADA assay at baseline with all post first dose ADA results negative, OR a positive response at baseline with all post first dose ADA responses less than 9-fold over baseline titer levels.
- Treatment-emergent response, defined as an ADA positive response in the ADA assay post first dose when baseline results are negative or missing. The treatment-emergent responses will be further characterized as Persistent, Indeterminate or Transient.
 - Persistent Response – Treatment-emergent ADA positive response with two or more consecutive ADA positive sampling time points, separated by at least 16-week period (based on nominal sampling time), with no ADA negative samples in between, regardless of any missing samples.
 - Indeterminate Response –Treatment-emergent ADA positive response with only the last collected sample positive in the ADA assay, regardless of any missing samples.
 - Transient Response –Treatment-emergent ADA positive response that is not considered persistent or indeterminate, regardless of any missing samples.

- Treatment-boosted response, defined as a positive response in the ADA assay post first dose that is greater than or equal to 9-fold over baseline titer levels, when baseline results are positive

Titer categories (Maximum titer values)

- Low (titer <1,000)
- Moderate (1,000 ≤ titer ≤ 10,000)
- High (titer >10,000)

The following analysis will be provided:

- Number (n) and percent (%) of ADA-negative subjects (pre-existing immunoreactivity or negative in the ADA assay at all time points) by treatment groups
- Number (n) and percent (%) of treatment-emergent ADA positive subjects by treatment groups and ADA titer categories and at the
 - Number (n) and percent (%) of persistent treatment-emergent ADA positive subjects
 - Number (n) and percent (%) of indeterminate treatment-emergent ADA positive subjects
 - Number (n) and percent (%) of transient treatment-emergent ADA positive subjects
- Number (n) and percent (%) of treatment-boosted ADA positive subjects by treatment groups and ADA titer categories

Listing of all ADA titer levels will be provided for subjects with pre-existing, treatment-emergent and treatment-boosted ADA response.

5.10.1. Analysis of Neutralizing Antibody (NAb) Data

The absolute occurrence (n) and percent of subjects (%) with NAb status in the NAb analysis set will be provided by treatment groups.

5.11. Association of Immunogenicity with Exposure, Safety and Efficacy

5.11.1. Immunogenicity and Exposure

Potential association between immunogenicity variables and systemic exposure to will be explored by treatment groups. Plots of drug concentration time profiles may be provided to examine the potential impact of ADA response status, titer, and NAb on these profiles.

5.11.2. Immunogenicity and Safety and Efficacy

Potential association between immunogenicity variables and safety may be explored with a primary focus on the following safety events during the TEAE period:

- Injection site reaction (serious or severe and lasting 24 hours or longer)
- Hypersensitivity (SMQ: Hypersensitivity [Narrow])

- Anaphylaxis reaction (SMQ: Anaphylaxis [Narrow])

Potential association between immunogenicity variables and efficacy endpoints may be explored (e.g., scatter plot or spaghetti plot).

The safety and efficacy analyses mentioned above will be conducted using the following categories:

- ADA positive subjects: subjects with treatment-emergent or treatment-boosted response.
- ADA negative subjects: subjects with pre-existing immunoreactivity or negative in the ADA assay at all time points.
- Subjects with persistent treatment-emergent ADA response
- NAb positive subjects: ADA positive subjects who were positive in the NAb assay at any time point analyzed.
- Maximum post-baseline titer in treatment-emergent or treatment-boosted ADA positive subjects:
 - Low (titer <1,000)
 - Moderate (1,000 ≤ titer ≤10,000)
 - High (titer >10,000)

6. DATA CONVENTIONS

The following analysis conventions will be used in the statistical analysis.

6.1. Definition of Baseline for Efficacy/Safety Variables

Unless otherwise specified, the Baseline assessment for all measurements will be the latest available measurement taken prior to the administration of study drug.

6.2. Data Handling Convention for Efficacy Variables

Rules for handling missing RT-qPCR test results for primary and secondary efficacy variables are described in Section [5.7.1](#).

6.3. Data Handling Convention for Missing Data

Missing data will not be imputed in listings. This section includes the methods for missing data imputation for some summary analyses, if necessary.

Date and Time of Study Treatment Injection

Since the study drug is administered at the site, the date and time of study drug administration are filled in eCRF. No missing data is expected. The information is filled in eCRF.

Adverse Event

If the severity of a TEAE is missing, it will be classified as “severe” or “Grade 3” in the frequency tables by intensity of TEAEs. If the assessment of relationship of a TEAE to the investigational product is missing, it will be classified as related to study drug.

When the partial AE date/time information does not indicate that the AE started prior to study treatment or after the TEAE period, the AE will be classified as treatment-emergent.

Medication/Procedure

If a medication date or time is missing or partially missing and it cannot be determined whether it was taken prior or concomitantly or stopped prior to the first study treatment administration, it will be considered as concomitant medication/procedure by imputing the start date on the date of first study treatment administration.

Potentially Clinically Significant Value (PCSV)

If a subject has a missing baseline value, this subject will be grouped in the category “normal/missing at baseline.”

For PCSVs with 2 conditions, one based on a change from baseline value and the other on a threshold value or a normal range, with the first condition being missing, the PCSV will be based only on the second condition.

For a PCSV defined on a threshold and/or a normal range, this PCSV will be derived using this threshold if the normal range is missing; e.g., for eosinophils the PCSV is >0.5 giga/L or $>\text{ULN}$ if $\text{ULN} \geq 0.5$ giga/L. When ULN is missing, the value 0.5 should be used.

Measurements flagged as invalid by the laboratory will not be summarized or taken into account in the computation of PCSVs.

